## 1. INTRODUCTION

This statistical analysis plan (SAP) defines the statistical analysis methods and data preparations to be used by [REDACTED] biostatistics department in the analysis and presentation of data for Galapagos protocol number GLPG1690-CL-204 entitled ‘A Phase 2a randomized, double-blind, placebo-controlled, multi-center study to evaluate the efficacy, safety, and tolerability of orally administered GLPG1690 for 24 weeks in subjects with systemic sclerosis’.

The statistical analysis will process and present the results following the International Council for Harmonization (ICH) standards, particularly the ICH-E3, ICH-E6 and ICH-E9 guidelines, and [REDACTED] Global Biostatistics and Programming standard operating procedures (SOPs). This SAP is created based on the latest Clinical Study Protocol (CSP) as referred in section 2.4. Technical details on derivations and mock Tables, Listings and Figures (TLFs) will be presented in a separate document.

[REDACTED]

Only data collected for the GLPG1690-CL-204 (CL-204) will be stored in CL-204 SDTM and ADaM datasets, data collected after the date of first Investigational Medicinal Product (IMP) dose taken during the open-label extension phase of the study, which is described in protocol number GLPG1690-CL-206 (CL-206) will be excluded. The previous day before this date will be regarded as the end date of the CL-204 study for those subjects who start the CL-206 study, while the last contact date will be regarded as the end of CL-204 study for those subjects who do not roll over into CL-206 study. Data from the CL-204 and CL-206 protocols will be collected on the same database. At the end of the CL-204 study (i.e. when all subjects have met the CL-204 protocol definition of end of trial), a snapshot of the database will be used for the clinical study report (CSR) for CL-204. Any changes to the data and additional data that become available (only expected for concomitant medications and adverse events) captured after the data snapshot for CL-204 CSR will be reported in the CL-206 CSR, which will include cumulative data across both protocols.

## 2. STUDY DESIGN AND OBJECTIVES

### 2.1. STUDY OBJECTIVES

#### Primary Objective

- To evaluate the efficacy of GLPG1690 as evaluated by modified Rodnan skin score (mRSS) compared to placebo over 24 weeks for the treatment of subjects with systemic sclerosis

#### Secondary Objective

- To evaluate the safety and tolerability of GLPG1690 compared to placebo over 24 weeks in the treatment of subjects with systemic sclerosis

---

### Other Objectives

- | [REDACTED]
- | [REDACTED]
- | [REDACTED]
- | [REDACTED]
- | [REDACTED]
- | [REDACTED]

## 2.2. STUDY ENDPOINTS

### Primary Endpoint

- Change from baseline in mRSS over 24 weeks, i.e. over the entire treatment period as well as at each timepoint.

### Secondary Endpoint

- Incidence of treatment-emergent adverse events (TEAEs), serious adverse events (SAEs), adverse events (AEs), and tolerability of GLPG1690 over 24 weeks

### Other Endpoints

- | [REDACTED]
- | [REDACTED]
- | [REDACTED]
- | [REDACTED]
- | [REDACTED]
- | [REDACTED]

---

## 2.3. STUDY DESIGN

This is a randomized, double-blind, parallel-group, placebo-controlled, multi-center, Phase 2a study designed to evaluate the efficacy, safety, and tolerability of a 600 mg once daily (q.d.) dose of orally administered GLPG1690 over 24 weeks in approximately 30 adult subjects with a confirmed diagnosis of systemic sclerosis.

At Day 1/Visit 2 (baseline), subjects will be randomized in a 2:1 ratio to GLPG1690 600 mg q.d. taken as three film-coated tablets of 200 mg, or matching placebo q.d. administered for 24 weeks in addition to background treatment as defined in the protocol.

The subjects will visit the clinical study center at screening/Visit 1 (Day -28 to Day -1), Day 1/Visit 2 (baseline), Day 15 (Week 2/Visit 3), Day 29 (Week 4/Visit 4), Day 57 (Week 8/Visit 5), Day 113 (Week 16/Visit 7), Day 169 (Week 24/Visit 9), and, if applicable, the early discontinuation (ED) visit. At Weeks 12 (Visit 6) and 20 (Visit 8), a phone call will be made to assess safety. In addition, a follow-up visit will be planned 4 weeks after the last administration of IMP (Day 197 [Week 28]) (i.e. Follow-up Visit 1) and a second follow-up visit will be planned 12 weeks after the last administration of IMP (Day 253 [Week 36]) (i.e. Follow-up Visit 2). Additional unscheduled visits are allowed for any safety assessments if clinically indicated (see protocol Section 6.2). The end of the study (EoS) is reached when the last visit of the subject is performed. The assessments performed at each visit are detailed in the Schedule of Activities (see [Appendix 1](#)).

A schematic diagram of the clinical study design, procedures, and stages is provided in Figure 1 (section [2.5](#)).

Each subject will be in the study for up to approximately 40 weeks (up to 4 weeks of screening, 24 weeks of treatment, and 12 weeks of follow-up).

### Open-label Extension

Subjects who completed the Week 24 visit will be offered treatment with GLPG1690 in an optional open-label extension (OLE), provided regulatory and Independent Ethics Committee (IEC)/Institutional Review Board (IRB) approvals for such an extension is granted. In this case, the follow-up visits as scheduled in protocol GLPG1690-CL-204, will not be performed for these subjects.

The analysis methods of the OLE study is not presented in this SAP and will be described in a separate SAP.

## 2.4. CSP AND CSP AMENDMENTS

Protocol Versions	Date (ddMMMyyyy)
Version 1	31JUL2018
Version 2	20AUG2018
Amendment 1: Version 3	13NOV2018
Amendment 2: Version 4	31JUL2019
Amendment 3: Version 5	28APR2020

[figure not shown]
Protocol Amendments	Date (ddMMMyyyy)
Country Specific Amendment	12MAR2019

This SAP was based on the latest version of the protocol that was available at the time of its finalization.

## 2.5. FLOW CHART

A schematic diagram of the clinical study design, procedures, and stages is provided in [Figure 1](#).

**Figure 1: Schematic Study Overview**

D=Day, FU=Follow-up, V=Visit, W=Week.

\* This will be a phone call to assess safety (no clinical study center visit).

## 2.6. SAMPLE SIZE JUSTIFICATION

Sample size was based on empirical considerations. The number of subjects (30) included in this study should give reasonable precision around the estimates derived for the efficacy evaluation.

The primary endpoint of the study is the change from baseline in mRSS over 24 weeks.

Considering 20 and 10 subjects in the GLPG1690 and placebo arm, respectively, and a common standard deviation (SD) of 5 on the change from baseline in mRSS, the Minimal Clinically Important Difference (MCID) of 4.7, and taking into account a 10% dropout, the probability to observe a treatment effect of more than 4 points is 63%.

---

## **2.7. RANDOMIZATION AND BLINDING**

### **Randomization**

This is a randomized, double-blind clinical study. At screening, subjects will be assigned a subject identification. When a subject is confirmed to be eligible for the clinical study, the subject will be randomized. Allocation of each subject to a given treatment will be done using a centralized electronic system (interactive web response system [IWRS]). Subjects will be randomized in a 2:1 ratio to receive GLPG1690 600 mg q.d. or matching placebo, respectively.

For each subject at each clinical study center visit, the clinical study center will contact the IWRS for the appropriate treatment number to be assigned. The medication kit(s) will contain the relevant IMP for the period until the next clinical study center visit.

Subjects and the entire clinical study team, including the investigators, clinical study coordinators, [REDACTED] and sponsor personnel are blinded to treatment assignment.

### **Blinding and Unblinding**

Blinded and packaged medication will be provided to the clinical center.

The blind can be broken by the investigator via IWRS only if the investigator deems it necessary for the safety of a subject. Further details are included in section 4.6.2 of the protocol.

Code-break information (via IWRS vendor/randomization list) will be provided to the bioanalytical laboratory responsible for plasma drug determination sample analysis, and to the sponsor pharmacovigilance lead for SAE reporting purposes.

Biostatistics team will be unblinded at the time of the primary analysis which is scheduled when all patients completed the Week 24 visit and data is locked for the primary analysis. Only study team members included in the analyses and reporting activities will become unblinded at the time of the primary analysis in case it is different from the CL-204 study full analysis with regards to timing.

## **3. GENERAL METHODOLOGY**

### **3.1. ANALYSIS SETS**

The analysis sets used in the statistical analyses are detailed in the following subsections. The analysis set will always be indicated in a subtitle in the TLF.

#### **3.1.1. All Screened Analysis Set**

All subjects who signed and dated an informed consent form (ICF) and underwent screening assessments to check whether or not they are eligible to participate in the clinical study.

#### **3.1.2. All Randomized Analysis Set**

All enrolled subjects who were randomized into the clinical study. Subjects will be analyzed according to the treatment arm to which they were randomized.

---

### 3.2. RANDOMIZED VERSUS ACTUAL TREATMENT GROUP

For all subject data, the treatment group as assigned by the randomization will be used in the analysis (i.e., as-randomized analysis).

Differences between the randomized and actual treatment group will be explained in the CSR.

### 3.3. ANALYSIS PERIODS AND ANALYSIS TIME POINTS

#### 3.3.1. Relative Day

The timing of an assessment or an event relative to a reference date will be calculated as follows:

*Relative day (DY)*

= *concerned date* – *reference date* + 1 day, when *concerned date* ≥ *reference date*

= *concerned date* – *reference date*, when the *concerned date* < *reference date*

- The *reference date* is the date of the first IMP intake, unless specified otherwise.
- The *concerned date* could be the measurement date of the assessment, or the start or end date of the event.
- *Date* implies a complete date. If the date is (partially) missing, the relative day will be missing.

Exception: if the end date of an event is fully missing at database lock (in case of an interim analysis) or at the subject's study termination, the event will be considered as ongoing. The end date will be imputed by the database cutoff date or the date of last visit for cases where subject terminated study. In listing, the duration will be printed as "> X days".

#### 3.3.2. Duration

The duration of an assessment or an event will be calculated as follows:

*Duration (days)* = *end date* – *start date* + 1 day

- *Date* implies a complete date. If the date is (partially) missing, the duration will be missing.

Exception: if the end date of an event is fully missing at database lock (in case of an interim analysis) or at the subject's study termination, the event will be considered as ongoing. The end date will be imputed by the database cutoff date or the date of last visit for cases where subject terminated study. In listing, the duration will be printed as "> X days".

#### 3.3.3. Analysis Periods

All event-type data (e.g., AEs) and assessments will be allocated to analysis periods according to [Table 1](#).

**Table 1: Analysis Periods**

Analysis Period	Start Analysis Period	End Analysis Period
Screening	Date of signing the ICF.	Date of first IMP intake - 1 day
Treatment	Date of first IMP administration.	For subjects not entering CL-206 study: date of last intake of IMP + 30 days.  For subjects who entered the CL-206 study: the date of last intake of IMP + 30 days or the date of first OLE IMP administration (excluded), whichever comes first.
Post-Treatment	End date of the treatment period + 1 day.	Date of last contact in CL-204 study. For subjects who entered the CL-206 study this will be the date of first OLE IMP administration.

ICF: informed consent form

The last analysis period will always end on the date of last contact, collected on the Study Completion/Discontinuation of Study eCRF page, whichever is earliest.

### 3.3.4. Analysis Windows

All assessments including data collected on unscheduled visits, will be allocated to analysis visits (time windows) based on the relative day of the assessment (see section 3.3.1) and according to the algorithm in Table 2. TFLs will present the analysis visits when analysis is derived.

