**Table 2: Analysis Windows**

Analysis label	Visit	Target Day	Interval Lower Bound	Interval Upper Bound
Vital signs, Clinical Laboratory tests				
Baseline*		1	-INF	1
Week 2		15	2	22
Week 4		29	23	43
Week 8		57	44	85
Week 16		113	86	141
Week 24		169	142	197
Week 28		198	198	+INF
12-Lead ECG				
Baseline*		1	-INF	1
Day 1		1	1	2
Week 2		15	3	64
Week 16		113	65	141
Week 24		169	142	197
Week 28		198	198	+INF
mRSS				
Baseline*		1	-INF	1
Week 4		29	2	43
Week 8		57	44	85
Week 16		113	86	141
Week 24		169	142	197
Week 28		198	198	+INF

---

IMP administration. If no triplicate (or duplicate) results are available before the first dose, the last value before first study drug administration will be used.

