### **Selection of Visits**

Per parameter, analysis visit and timepoint, the value closest to the target date will be used in analysis tables and figures. Other values will be listed only. If more than one value is located at the same distance from the target day, then the latest in time will be selected. If there are two values on the same day and no time indicating which one is last, the average of the two will be calculated.

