## 5. STATISTICAL ANALYSES

### 5.1. CHANGES TO THE PLANNED ANALYSES, NOT COVERED BY PROTOCOL AMENDMENTS

- All Enrolled Analysis Set will not be used for the analyses so not included in SAP.
- All Randomized Analysis Set will be used for the presentation and summary of the baseline assessments to better interpret the study data.
- Definition of Per-Protocol Analysis Set was slightly modified within this SAP text as unblinding will occur at the time of primary analysis, i.e. not at the same time of database lock.
- Definition of Per-Protocol Analysis Set was modified to exclude subjects who had mRSS assessment at Week 24 outside of the original time window of [142, 183] study day.

- An additional sensitivity analysis for the primary endpoint was added where for subjects that did not have a Week 24 mRSS assessment at all within the extended window, but possibly in the Week 28 - Week 32 interval, their Week 28 result will be allocated to Week 24 analysis visit.

---

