## 5.3. EFFICACY ANALYSES

Efficacy analyses will be performed on the FAS. To investigate the impact of non-compliance and protocol violators, a Per-Protocol analysis will also be performed for the primary endpoint, if more than 10% of the subjects have at least one major protocol deviation leading to exclusion to the PP Analysis Set.

Tabulations will be shown per treatment group.

---

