**5.3.3. Sensitivity of Primary Endpoint**

**5.3.3.1. Derived mRSS**

**5.3.3.1.1. Definition**

If more than 10% of subjects have missing mRSS total score at Week 24, then the change from baseline in derived mRSS will be analyzed over 24 weeks to confirm the results of the primary efficacy analysis.

There will be an additional sensitivity analysis for subjects that did not have a Week 24 at all within the extended window, but possibly in the Week 28 - Week 32 interval. These subjects will be off IMP in that period. The primary endpoint analysis will be repeated including the closest mRSS assessment to the original Week 24 target (Day 169) up to and including Week 32 (Day 225).

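### SAP Table 2 ends Week 24 on Day 197, the planned day of Follow-up Visit 1, so an on-schedule off-drug visit is filed as Week 24 and the subject can lose the Week 28 by-visit value

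*SAP*

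**What the plan says.** SAP 3.3.4 files every assessment, unscheduled ones included, by study day: they "will be allocated to analysis visits (time windows) based on the relative day of the assessment". For mRSS, Table 2 gives Week 24 a target of Day 169 and limits of Days 142 to 197. The next row reads "Week 28 198 198 +INF" (label, target, lower limit, upper limit). The Week 24 and Week 28 limits are the same for laboratory tests, vital signs and ECG. Within a window, "the value closest to the target date will be used in analysis tables and figures. Other values will be listed only", and ties go to the later value.

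SAP 2.3 says that "a follow-up visit will be planned 4 weeks after the last administration of IMP (Day 197 [Week 28", so Day 197 is the planned day of FU1. Protocol 6.1 allows 7 days either side of 28 days after the last dose. Subjects who enter the extension have no follow-up visits.

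Three other places bear on the point.

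- SAP 5.1 adds a sensitivity analysis for subjects with no Week 24 mRSS in the extended window: "their Week 28 result will be allocated to Week 24 analysis visit". SAP 5.3.3.1.1 remarks of them: "These subjects will be off IMP in that period".
- SAP 5.1 changes the Per-Protocol set to "exclude subjects who had mRSS assessment at Week 24 outside of the original time window of [142, 183] study day". SAP 5.3 runs that analysis only "if more than 10% of the subjects have at least one major protocol deviation leading to exclusion to the PP Analysis Set".
- SAP 4 bases the primary-analysis outputs on data up to the Week 24 visit. It does not say whether FU1 records already collected are cut.

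**The concern.** The visit that the SAP itself calls Week 28 is, on its planned day, analysed as Week 24. Nothing in the visible text conditions the window on nominal visit or on the last dose.

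The main consequence is a gap in the off-drug summaries. FU1 is the scheduled post-treatment assessment of mRSS, laboratory tests, vital signs and ECG, and none of these is scheduled again at Follow-up Visit 2. A subject seen on the planned day or earlier usually drops out of the Week 28 tables and plots, while one seen a day later stays in. Only non-rollover subjects have FU1, so this group is already small.

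The second consequence is rarer. Where no Visit 9 mRSS exists, a score taken after stopping drug can stand as the Week 24 value, and a one-day difference in FU1 timing decides whether it enters the main model or only the sensitivity analysis.

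**Working it through.** **Inputs**

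- Day convention (SAP 3.3.1): the first dose is Day 1, so week w falls on Day 7w + 1. Week 24 = 169, Week 28 = 197 and Week 32 = 225, matching the days that the SAP prints.
- Windows (Table 2): Week 16 = Days 86-141; Week 24 = Days 142-197, target 169; Week 28 = Day 198 onward, target 198.
- Visit 9 (Protocol 6.1): ±4 days, so Days 165-173; under the COVID-19 rule ±28 days, so Days 141-197.
- FU1 (Protocol 6.1): last dose + 21 to + 35 days.
- Assumption: the last dose is on the day of Visit 9, as the planned Day 197 = 169 + 28 implies.

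**Where the bound comes from (inference).** 169 + 28 = 197, the end of the COVID-19 extension. The earlier bound, Day 183, is the midpoint (169 + 197)/2.

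**1. Last dose on Day 169.** FU1 may fall on Days 190-204. Days 190-197 map to Week 24: 8 of 15, including the planned day.

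**2. All on-time combinations.** There are 9 Visit 9 days × 15 FU1 days = 135. For Visit 9 on day v, FU1 lands in Week 24 when its lag is at most 197 − v. For v = 165 to 173 that gives 12 + 11 + 10 + 9 + 8 + 7 + 6 + 5 + 4 = 72 (53%). With FU1 at exactly + 28, it happens for Visit 9 on Days 165-169 and not on Days 170-173.

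**3. Does FU1 replace an on-time Visit 9?** The earliest FU1 is Day 165 + 21 = 186, which is 17 days from target. Visit 9 is at most 4 days from target. FU1 is chosen in 0 of 135, so in all 72 it is only listed.

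**4. Visit 9 mRSS missing.** In the same 72 of 135, FU1 is the only score in the window and becomes the Week 24 value. All lie on Day 186 or later, so the [142, 183] Per-Protocol rule would exclude them if that analysis is run. An FU1 on Day 198 would enter Week 24 only in the sensitivity analysis.

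**5. Substitution that does not depend on Day 197** (FU1 at + 28)

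- COVID-19 Visit 9 moved earlier to day v: FU1 is chosen when v + 28 − 169 ≤ 169 − v, that is v ≤ 155, at least 14 days early. With FU1 at + 21 or + 35 the thresholds are 11 and 18 days. A Visit 9 on Day 141, the first day allowed, falls in the Week 16 window.
- Early stop with the early-discontinuation (ED) visit on the last-dose day: FU1 is the Week 24 value for last doses on Days 114-155, 42 days. For Days 114-141 (28 days) it is the only score in the window. For Days 142-155 (14 days) it is chosen over the ED score.
- These FU1 visits fall on or before Day 155 + 28 = 183. They would occur under the earlier window too, and they pass the [142, 183] rule.

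Illustration of size, on assumptions that the documents do not give (3 of 30 subjects stop early, last dose uniform over the 167 days from Day 2 to Day 168, all attend ED and FU1 on site): 3 × 42/167 = 0.75 subject, of which 3 × 14/167 = 0.25 has an ED score passed over.

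**6. Would another cut-off day do?** With bound 196, 11 + 10 + 9 + 8 + 7 + 6 + 5 + 4 + 3 = 63 of 135 are still lost. With bound 183, 0 of 135 are lost, but an on-drug Visit 9 delayed to Days 184-197 (14 days) would be filed as Week 28. No single day separates the two visits.

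**The case against.** The strongest reply is that little of importance is lost. The primary endpoint covers 24 weeks, and Week 28 is neither a primary nor a stated secondary endpoint. The Week 24 mRSS is untouched after an on-time Visit 9. Unselected values are still listed, worst-case safety tables include follow-up visits, and SAP 5.2.2 tabulates subjects per mRSS window. SAP 4 can be read as leaving completers' FU1 out of the primary run. All of this stands and limits the severity. It does not remove the misfiling: SAP 4 is not explicit, and the final analysis has no such cut.

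Three stronger readings are tempting, and the documents do not support them.

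- A reader might blame the Day 197 bound for every off-drug Week 24 score. Only the missing-Visit 9 route depends on it. At nominal timing, the early-stop and early COVID-19 routes come from allocation by study day alone.
- A reader might say that the SAP contradicts its own rule on off-drug scores. The added sensitivity analysis literally covers subjects with no score inside the extended window, and a Day 197 score is inside it. No visible text bars off-drug scores from Week 24. The tension is with the evident purpose of that analysis.
- A reader might require an ED score always to beat a later FU1 score. With last dose and ED on Day 142 and FU1 on Day 170, that prefers a score 27 days from target to one a day from it. Which to use is a choice of estimand, not the correction of an error.

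**Conclusion.** The point holds for the boundary. As printed, Table 2 files an on-schedule FU1 as Week 24, and 72 of 135 permitted day combinations leave no scheduled Week 28 value after an on-time Visit 9. It applies only to subjects who do not roll over. The Week 24 mRSS is affected through this boundary only when the Visit 9 score is missing. Off-drug Week 24 scores after early stops or early COVID-19 visits are a separate and smaller matter.

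The counts are shares of calendar days, equally weighted, not of subjects. The number of subjects with a substituted score cannot be computed from the documents and is probably below one. Two gaps in the copy qualify the conclusion. Part of the Table 2 footnote is missing (the visible part concerns baseline), so a further rule there is unlikely but not excluded. The full Per-Protocol definition is also absent, so only the day rule in SAP 5.1 was tested. Severity is minor to moderate.

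**What to change.** In SAP Table 2:

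1. Assign the nominal Visit 9 record on Days 141-197 to Week 24.
2. For subjects who completed treatment, including those whose Visit 9 was moved under the COVID-19 rule, assign the nominal FU1 record to Week 28 whatever its study day. Set the Week 28 target to Day 197.
3. Allocate other records on Days 184-197, such as unscheduled ones, by the date of the last IMP dose: on or before it to Week 24, after it to Week 28. Do not simply restore Day 183, for the reason in step 6 of the working.
4. For early discontinuers, keep the stated selection rule for ED and FU1 records. Flag any Week 24 mRSS that is an off-drug FU1 score, and repeat the MMRM without such values as a sensitivity analysis.

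In SAP 4, state whether FU1 records are in the primary-analysis data cut.

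With items 1 and 2, none of the 135 on-time combinations loses its Week 28 value, and a delayed Visit 9 up to Day 197 stays in Week 24. The cost is table wording, one sentence in SAP 4, minor programming and one extra sensitivity run. No new data are needed.
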